8.6.4.1 Late Bolus Meal Challenge Safety and CGM Subgroup Analysis

Two challenges are expected per subjects per treatment period for a total of four challenges, therefore agreement of outcomes will need to be assessed. For continuous outcomes, two sets of Pearson's correlation coefficients will be calculated to measure concordance: one restricted to each treatment period (higher range target and lower range target), and a single coefficient for all four challenges. For categorical outcomes, a Cohen's kappa statistic for agreement or a similarly appropriate statistic will be calculated and presented to describe agreement/dependence of outcomes by individual subjects. Results will be compared by treatment period and across treatment periods.

The analyses described in sections 8.6.1, 8.6.2, and 8.6.3 will be repeated for subjects included in the late bolus meal challenge set. For the CGM outcomes, the mean of the CGM metrics for the two late meal

bolus challenges within study period will be used to account for within-subject non-independence (i.e. one data value per subject per study period).

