- Diabetic ketoacidosis during study compared with data on DKA events reported by T1D Exchange clinic registry over a 3-month time period
- 3. Number of unanticipated adverse device effects
- 4. Number of other serious device-related adverse events

Secondary Endpoints:

- 1. All device-related adverse events
- 2. CGM hypoglycemia outcomes, compared between the three study time periods
 - a. Overall % time <54 mg/dL
 - b. Overall % time <70 mg/dL
- Times in ranges-overall (70-180 mg/dL, >180 mg/dL, >250 mg/dL, 70-140 mg/dL) compared between the three study time periods
- 4. Mean glucose compared between the three study time periods
- 5. Overall variability (CV and SD) compared between the three study time periods
- 6. Secondary endpoints 2 5 compared during daytime and nighttime, across the three study time periods
- 7. Secondary endpoints 2 5 as well as adverse events, during the study meal challenge periods, for late bolus feature use compared to normal bolus in the meal challenges.
- Time to intervention for hypo- or hyperglycemia during the study meal challenge periods, for late bolus feature use compared to normal bolus in the meal challenges.
- Number of interventions for hypo- or hyperglycemia during the study meal challenge periods for late bolus feature use compared to normal bolus in the meal challenges.
- 10. Subgroup Analysis for all metrics by age cohort, baseline HbA1c cohort, and target activity use (standard target, lower target, sleep activity, exercise activity)

Protocol Overview/Synopsis

After consent is signed, eligibility will be assessed.

Run-In Period:

Participants will return to clinic to undergo device training with the study CGM and a Control-IQ technology 1.5 pump. Training for both devices may be combined, or depending on comfort level of investigator and participant, participants may return for a second session to complete device training and begin the Control-IQ 1.5 run in period. The run-in period will end after 2 weeks of Control-IQ technology 1.5 use.

Participants will have a phone follow up phone call at 1 day, 3 days and 1 week after starting Control-IQ technology 1.5 use, and will return to clinic at two weeks to commence Control-IQ technology 2.0 training.

Treatment Periods:

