516 517 518	 Full bolus for the given carbohydrates and calculated correction, given 45 minutes after starting the meal, based on calculated bolus dose using the bolus calculator (with full amount of carbohydrates entered).
519 520 521	• Full bolus for the given carbohydrates and calculated correction, given 45 minutes after starting the meal, based on calculated bolus dose using the bolus calculator (with full amount of carbohydrates entered) AND enabling the late bolus feature to 45 minutes later.
522	For each meal challenge, participants will:
523 524	1. Be in a fasting state for two hours prior to consuming the last meal of the day, with the last manual insulin bolus more than two hours prior to the meal.

- 525 2. For participants age 6+, only begin the meal challenge if CGM glucose is between 70 mg/dL and 200 mg/dL, and CGM trend arrow is not down.
- For participants age 2-5, only begin the meal challenge if CGM glucose is between 70 mg/dL and 250 mg/dL, and CGM trend arrow is not down.
- 529 Subjects with hyperglycemia > 200mg/dL will reschedule their challenge for another time. If < 530 To mg/dL, carbohydrate treatment can be given, after which the meal challenge can continue.
 - 3. Pediatric participants age 2-5 should have a meal with at least 20 grams of carbohydrates. Participants age 6-13 should have a meal with at least 35 grams of carbohydrates. All other participants should have at least 50 grams of carbohydrates for the study meal challenges. *Each participant should use the same meal for all of their meal challenges in the study. Participants will be encouraged to use the same frozen entrée of their choice for consistency.*
 - 4. Do their best to complete the meal within 30 minutes of starting to eat.
 - 5. Write down the start and end time of eating the meal, as well as the meal content (to include amount of carbohydrate, protein and fat) on the study provided logbook.
 - 6. Bolus for the meal 45 minutes after starting to eat, entering the full carbohydrate amount and using the recommended dose from the bolus calculator. For one of the two challenges during a single treatment period, use the bolus calculator but do not change the bolus time. For the other challenge during the same treatment period, use the bolus calculator but change the bolus time to 45 minutes late.

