8.6.3 Analysis of CGM Endpoints

CGM metrics will be assessed in CGM analysis set, and computed for the Run-In and both Treatment Periods separately. CGM metrics will be computed per subject over 24 hours, during daytime (6am-11:59pm), and during nighttime (12am-5:59am), as well as by age cohort (adults/adolescents, children 6 – 13, and preschool), baseline HbA1c cohort (HbA1c at baseline of ≥ 7.5%,yes/no), and target activity use as specified by the device (standard target, lower target, sleep activity, and exercise activity). The main statistical comparison will be made between the three 2-week periods (Run In, Treatment

The main statistical comparison will be made between the three 2-week periods (Run In, Treatment Period at standard target, Treatment Period at lower target). The comparison will be pairwise – Run-in vs standard targe, Ru-in vs lower target, and standard vs lower target. The percent time in glycemic ranges will be calculated as the number of measurements in the specified range divided by the total number of measurements for which it can be determined whether or not the measurement was in specified range.

The "Low" and "High" CGM readings will be included in all analyses. Percent time will be compared using a paired t-test assuming sufficient normality assumptions hold, otherwise an appropriate non-parametric method will be utilized.

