8.6.4.2 Time to Intervention Analysis

1005

1006

1007

1018

1031

1032

1033

1039 1040

1041

Time to intervention for both hypo- or hyperglycemia during the study meal challenge periods will be 1008 summarized. Time to intervention is defined as the time (in minutes) from start of meal until the first 1009 treatment is given as defined in Section 6.2. If multiple interventions are needed to treat hypo- or 1010 hyperglycemia during the meal challenge, only time to the earliest intervention will be summarized. The 1011 results will be presented using general summary statistics, as well as utilizing Kaplan-Meier time-to-event 1012 analysis where subjects who complete the meal challenge without requiring any intervention will be right-1013 censored. A cox proportional hazards model will be fit comparing time to intervention between the two 1014 active treatment periods. A p-value from the log-rank test will be used to evaluate whether there is 1015 evidence of a difference between the two target ranges with respect to time to intervention. Results will be 1016 compared by treatment period and across treatment periods. 1017

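### The late-bolus versus normal-bolus contrast of secondary endpoint 7 is averaged away in section 8.6.4.1, and no meal-challenge analysis uses starting glucose

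*Combined protocol and SAP*

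**What the plan says.** - **Declared contrast.** Secondary endpoint 7 (synopsis and section 8.4) covers the CGM outcomes and adverse events for "late bolus feature use compared to normal bolus in the meal challenges".
- **Planned analysis.** Section 8.6.4.1 states that "The analyses described in sections 8.6.1, 8.6.2, and 8.6.3 will be repeated" in the challenge set. In section 8.6.3, "Percent time will be compared using a paired t-test assuming sufficient normality assumptions hold", with a non-parametric fallback. The comparisons there are between study periods, and no covariate is named.
- **Unit of analysis.** For challenge CGM metrics, 8.6.4.1 takes the mean of the two challenges within a period, giving "one data value per subject per study period".
- **Other challenge analyses.** In section 8.6.4.2, "A cox proportional hazards model will be fit comparing time to intervention between the two" treatment periods, with neither a covariate nor a bolus-type term. Section 8.6.4.3 only summarises intervention counts.
- **Entry glucose (section 5.1.1, step 2).** "For participants age 6+, only begin the meal challenge if CGM glucose is between 70 mg/dL and 200 mg/dL". The line for age 2-5 allows 70-250 mg/dL, yet a following sentence with no age limit sends anyone above 200 mg/dL to reschedule. A start after a treated low is allowed.
- **Conduct (section 5.1.1).** Time zero is the first bite. In both challenges the bolus comes 45 minutes later, and only then do the two differ. One challenge of each type is done per period, in no stated order. The same meal is to be used throughout.
- **Data.** A working CGM is required before each challenge (5.1) and device files are collected (9.1). The logbook instruction is to "Write down the start and end time of eating the meal, as well as the meal content"; glucose is not on that list.

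**The concern.** The meal challenges are where the late bolus feature is tested, and the synopsis excludes challenge data from the overall CGM metrics. If section 8.6.4 does not estimate late-feature minus normal-bolus, endpoint 7 has no specified analysis, and the method will be chosen after the data are in.

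Once the contrast is specified, starting glucose matters. It is likely to affect time high or low over the next 3-5 hours, and glucose at the bolus enters the calculated correction. A participant's two challenges take place on different evenings, at least 48 hours apart, with pump settings open to adjustment in between (3.7). With no random order stated, one type could tend to come first, or to be done on evenings with different starting glucose. An unadjusted difference would attribute that to the feature.

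**Working it through.** **1. What 8.6.4.1 estimates.** Challenges occur only under Control-IQ 2.0 (schedule of visits, footnote 1), so the run-in comparisons of 8.6.3 have no challenge data. What remains is standard versus lower target. For participant *i* at target *t*, write L for the late-feature value and N for the normal-bolus value:

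- Endpoint 7 needs L(i,t) − N(i,t).
- Section 8.6.4.1 analyses [L(i,t) + N(i,t)] / 2, compared between targets.

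The difference L − N cannot be recovered from that average. The Pearson and kappa statistics in the same section describe agreement, not a mean difference.

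**2. Reproducing a figure.** The documents give no power, effect size or SD for the challenges; section 8.3 says the sample size has no statistical basis. The only figure to check is 30 + 30 + 12 = 72 completers, which is correct. Everything below rests on assumptions.

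**3. Random differences in starting glucose.** Assume starting glucose is uniform over 70-200 mg/dL and independent between challenges.

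- SD = 130/√12 = 37.5; SD of a within-participant difference = 37.5 × √2 = 53.1
- One pair each from 72 participants: SE = 53.1/√72 = 6.25, 95% range ±12.3 mg/dL
- Both targets averaged: SE = 37.5/√72 = 4.42, 95% range ±8.7 mg/dL

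This variation is already in the paired standard error. It costs precision and does not bias.

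**4. Precision gained.** Let r be the correlation between the within-participant differences in outcome and in glucose. The large-sample SE ratio is √(1 − r²).

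| r | SE ratio | CI narrower by | 72 adjusted pairs equal (72/(1 − r²)) |
|---|---|---|---|
| 0.2 | 0.980 | 2.0% | 75 unadjusted |
| 0.3 | 0.954 | 4.6% | 79 |
| 0.5 | 0.866 | 13.4% | 96 |

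**5. Cost of estimating the slope.** With k covariates the variance ratio is (1 − r²)(n − 2)/(n − 2 − k).

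| n, k | r = 0.2 | r = 0.3 | r = 0.5 |
|---|---|---|---|
| 72, glucose only | 0.97 | 0.92 | 0.76 |
| 12, glucose only | 1.07 | 1.01 | 0.83 |
| 12, glucose and carbohydrate | 1.20 | 1.14 | 0.94 |

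At n = 12 with one covariate, break-even is 1 − r² = 9/10, so r = 0.32.

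**6. Systematic differences.** Assume a slope of 0.2 points of time in range per mg/dL, residual SD 15 per challenge, 72 pairs and no true effect (implied r = 0.45; 4,000 simulated runs). Shifted values are truncated at 200, so the realised shift is s − s²/260: 9.6 for s = 10 and 18.5 for s = 20. Expected biases are 0.2 × 9.6 = 1.9 and 0.2 × 18.5 = 3.7 points, in line with the simulation.

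| Shift (mg/dL) | Unadjusted bias (points) | Rejection, unadjusted | Rejection, adjusted |
|---|---|---|---|
| 0 | 0.0 | 5.6% | 5.1% |
| 10 | −1.8 | 9.6% | 4.6% |
| 20 | −3.6 | 25% | 5.0% |

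**7. Which glucose value.** The 70-200 limit applies at first bite, and nothing bounds glucose 45 minutes later. First-bite glucose precedes the whole outcome window. Bolus-time glucose precedes the point where the challenges diverge, but it lies inside the window of section 8.6.4: 45/300 = 15% of the 5-hour window and 45/180 = 25% of the 3-hour window come before it.

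**The case against.** A paired comparison is valid without covariates, and pairing plus the same-meal rule already remove much of the variation. Section 8.2 declares no formal hypotheses and bars formal inference from the p-values; section 8.1 names the paired t-test only as an example, so a model is not excluded. The gain may be only a few percent, and in the preschool cohort a covariate can lose precision. Linear adjustment also suits skewed, near-zero outcomes such as % time <54 mg/dL poorly.

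All of this stands, and it limits the point to one covariate, a pooled slope and a supporting unadjusted analysis. It does not supply the missing contrast, nor does pairing protect against a systematic difference between challenge types when no random order is stated.

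Three stronger readings are tempting:
- *Chance imbalance in starting glucose biases the estimate.* It does not: with no systematic shift, the unadjusted test was unbiased and rejected at 5.6%.
- *The trial already records glucose at the bolus.* The documents support only that it can be derived from the CGM files.
- *Logged carbohydrate should be a covariate too.* Each participant is told to use the same meal, so its within-participant difference should be near zero.

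**Conclusion.** The point holds in limited form. Section 8.6.4.1 as written does not estimate the contrast that endpoint 7 declares, and no challenge analysis uses starting glucose. Both follow from the text.

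The size of the benefit does not. At n = 72 it is a 2-5% narrower interval at r = 0.2-0.3 and 13% at r = 0.5, with r assumed, and slightly less once the estimated slope is paid for. Bias needs a systematic starting-glucose difference between challenge types. The documents leave that possible but do not show that it will occur; the 10 and 20 mg/dL shifts are illustrations.

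A reader might infer that the challenge results would be invalid without adjustment. The documents do not support that: the study is exploratory, and an unadjusted paired difference, once specified, is a legitimate estimate. The change is a cheap improvement that should be made before analysis.

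**What to change.** In section 8.6.4.1:

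1. Keep one value per challenge. Estimate late-feature minus normal-bolus within participant, in one mixed model over both targets, with a participant random effect and terms for target, period, challenge order and bolus type. Section 8.1 assumes no period or carryover effects; say that these terms are included for this contrast.
2. Add glucose derived from the CGM files as the single covariate: either first-bite glucose with the existing outcome window, or bolus-time glucose with the window starting at the bolus. Choose one in advance. Do not use bolus-time glucose to adjust the comparison of targets, because the assigned target may affect it.
3. Take the slope from the pooled model and do not estimate it separately in the 12 preschoolers.
4. Leave carbohydrate out, or keep it as a sensitivity analysis.
5. Report the unadjusted paired difference as support. Rely on it, or on a non-parametric method, for skewed outcomes such as % time <54 mg/dL.

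In section 5.1.1, reconcile the 70-250 mg/dL line for age 2-5 with the unqualified sentence on rescheduling above 200 mg/dL.

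Cost: SAP wording, a derived variable and a few lines of code. No new data are needed.

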2. CGM hypoglycemia outcomes, compared between the three study time periods 922 a. Overall % time <54 mg/dL 923 b. Overall % time <70 mg/dL 924 3. Times in ranges-overall (70-180 mg/dL, >180 mg/dL, >250 mg/dL, 70-140 mg/dL) compared 925 between the three study time periods 926 4. Mean glucose compared between the three study time periods. 927 5. Overall variability (CV and SD) compared between the three study time periods 928 6. Secondary endpoints 2 - 5 compared during daytime and nighttime, across the three study time 929 930 periods 7. Secondary endpoints 2 - 5 as well as adverse events, during the study meal challenge periods, for 931 late bolus feature use compared to normal bolus in the meal challenges. 932 8. Time to intervention for hypo- or hyperglycemia during the study meal challenge periods, for late 933 bolus feature use compared to normal bolus in the meal challenges. 934 935 9. Number of interventions for hypo- or hyperglycemia during the study meal challenge periods for late bolus feature use compared to normal bolus in the meal challenges. 936 10. Subgroup Analysis for all metrics by age cohort, baseline HbA1c cohort (HbA1c at baseline of > 937 7.5%, yes/no), and target activity use (standard target, lower target, sleep activity, exercise 938 939 activity). 940 8.5 Analysis Datasets 941 942 Safety analysis set: All participants who initiate the Treatment Period and use the study device at least one time (including training). 943 CGM analysis set: Any member of the Safety Analysis Set who has at least 24 hours of CGM data during 944 945 either Treatment Period. CGM data occurring within the meal challenge windows (from time of start of meal up to 5 hours afterwards [3 hours for age 2-5]) will not be used to determine whether a subject is 946 included in CGM analysis set or not. 947 948 Late bolus meal challenge set: Any member of the Safety Analysis Set who has at least 24 hours of CGM data during the Treatment Period, and who has at least 3 hours of CGM data for at least one meal 949 challenge. 950 8.6 Analysis of Endpoints 951 8.6.1 Analysis of the Safety Event Endpoints 952 953

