Safety events (not including CGM defined events defined in sections 6.2.2, 6.2.3, and 6.2.4) will be based on Safety analysis set, and tabulated for each primary endpoint as the number of events per participant, the number of participants with ≥ 1 event, and the rate of events per 100 person-years. A 95% confidence interval will be calculated for the rate of events per 100 person-years.

Since study eligibility excluded participants with 2 or more severe hypoglycemia or DKA events in the

Since study eligibility excluded participants with 2 or more severe hypoglycemia or DKA events in the prior 6 months, an unbiased comparison of the event rate during the Treatment Period with the pre-study event rate is not possible. Therefore, the severe hypoglycemia and DKA event rates will be compared with the T1D Exchange data, which reported the frequency of 1 or more severe hypoglycemia and DKA events in the prior 3 months. The proportion of participants with events during the Treatment Period (each

958

959

960

961

period separately) will be compared with the run-in period as well as with the T1D Exchange frequency.
Differences in proportions across the three study periods (two active treatments and the run in) will be estimated in a pairwise fashion, and statistical significance will be assessed using a normal approximation to a binomial distribution.

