8.6.4 Analysis of Late Bolus Meal Challenges

All analyses in section 8.6.4 will be conducted in the late bolus meal challenge analysis set. Data included in these analyses will be restricted to data during the meal challenge window (start of meal through 5 hours from meal imitation [3 hours for age 2-5]). The subgroups assessed will be the same as sections 8.6.1 − 8.6.3 (age cohort, baseline HbA1c cohort (HbA1c at baseline of ≥ 7.5%. yes/no), etc.)

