8.6.4.3 Number of interventions analysis

Number of interventions for hypo- or hyperglycemia during the study meal challenge periods will be summarized both overall and by type. The results will be presented using general summary statistics.

Type of intervention may include timing of intervention (during meal, less than one hour after starting meal, greater than one hour after meal start), the number of carbs administered (grouped in increments of 10 grams), and the timing of carb administration (less than 15 minutes per administration vs 15 minutes or more). The categories and groupings utilized for intervention type will be expanded or decreased based on the types of interventions that actually occur in the study. Results will be compared by treatment period and across treatment periods.

Type of intervention will be reviewed and assessed by the study Medical Monitor prior to analysis to define the logic that can be applied across all subjects (e.g., an intervention that occurred more than 15 minutes after the previous intervention will count as new intervention). Different logic may be applied to different age cohorts. This logic will be fully detailed in the final clinical study report.

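### Section 8.6.4.1 repeats the run-in, registry and person-year analyses on meal-challenge windows where they do not work, and Section 8.6.4.3 states no exposure unit for the number of interventions

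*Combined protocol and SAP*

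**What the plan says.** Section 8.6.4 sets the scope for all challenge analyses: "Data included in these analyses will be restricted to data during the meal challenge window". The window runs from the start of the meal for 5 hours, or 3 hours at ages 2-5.

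Section 8.6.4.1 then carries over the general analyses without change: "The analyses described in sections 8.6.1, 8.6.2, and 8.6.3 will be repeated for subjects included in the late bolus meal challenge set". Those sections contain:

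- **8.6.1:** for each primary safety endpoint, events per participant, "the number of participants with ≥ 1 event, and the rate of events per 100 person-years", with a 95% confidence interval. Each treatment period is then compared with the run-in and with a registry frequency covering three months.
- **8.6.2:** adverse event tabulations, with number and percent of participants.
- **8.6.3:** percent time in glucose ranges, compared pairwise by paired t-test. Besides run-in against standard target, the pairs are "Ru-in vs lower target, and standard vs lower target".

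Footnote 1 to the visit schedule and Section 5.1 place the challenges in the Control-IQ 2.0 treatment periods, two per period. Section 3.3 introduces the late bolus feature at Visit 6, after the run-in.

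For interventions, Section 8.6.4.3 says: "Number of interventions for hypo- or hyperglycemia during the study meal challenge periods will be summarized both overall and by type". It uses general summary statistics and compares treatment periods. Section 8.5 admits to the challenge set a participant with "at least 3 hours of CGM data for at least one meal" challenge, provided 24 hours of treatment-period CGM data also exist. Section 8.15 plans no imputation.

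**The concern.** Sections 8.6.1 to 8.6.3 were written for three two-week periods of continuous wear. Challenge windows are a few evening hours found in only two of those periods. Carried over unchanged, the run-in comparator disappears, the registry comparator covers a very different length of time, and the person-year scale rests on a small fraction of one year. The count of interventions also has no stated unit, so it could be per participant, per challenge or per hour.

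Secondary endpoints 7 (CGM outcomes and adverse events during challenges) and 9 (number of interventions) describe how safe late bolusing is. Section 8.2 says p-values will not be used for formal inference, so the descriptive rates and counts are the main output. If their denominator is chosen after the events are known, the same data can be reported on very different scales.

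**Working it through.** The documents give no event rate or precision figure for the challenge analyses, so there is no stated figure to reproduce. The check computes exposure directly.

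**Inputs**
- Planned completers (synopsis, Section 8.3): 30 aged 14+, 30 aged 6-13 and 12 aged 2-5. That is 60 aged 6+ and 12 aged 2-5, 72 in all.
- Challenges (Section 8.6.4.1): two per period, four in total. Run-in: none.
- Window (Section 8.6.4): 5 h, or 3 h at ages 2-5.
- Control-IQ 2.0 use: 28 days per participant.
- Assumptions: every completer does all four challenges with full windows; 365.25 days per year; exact Poisson limits, because Section 8.6.1 names no method.

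**Run-in contrasts.** Run-in challenge exposure is 0 challenges and 0 h. Each treatment period has 72 × 2 = 144 challenges. Run-in vs standard and run-in vs lower therefore cannot be formed. Standard vs lower can.

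**Registry comparison.** Window time per participant per period is 2 × 5 = 10 h (2 × 3 = 6 h at ages 2-5). Three months is 365.25/4 × 24 ≈ 2,190 h. The reference period is about 219 times the window time at age 6+ and about 365 times at ages 2-5.

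**Person-year rate**
- Window time: 60 × 4 × 5 + 12 × 4 × 3 = 1,200 + 144 = 1,344 h. Divided by 8,766 h per year, this is 0.153 person-years.
- Control-IQ 2.0 time: 72 × 28/365.25 = 5.52 person-years, 36 times the window time.
- Exact limits for x events over time T: lower = χ²(0.025; 2x)/(2T), upper = χ²(0.975; 2x+2)/(2T), each × 100.

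| Events | Window time, per 100 person-years | Control-IQ 2.0 time, per 100 person-years |
|---|---|---|
| 0 | 0 (upper limit 2,406) | 0 (upper limit 66.8) |
| 1 | 652 (17 to 3,634) | 18 (0.46 to 101) |

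Per challenge, one event is 1/288 = 0.35 per 100 challenges, a figure that needs no annualising.

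**Interventions.** Eligible participants can contribute from one to four challenges. Observed time can therefore run from a single window to 4 × 5 = 20 h (4 × 3 = 12 h at ages 2-5). Section 8.6.4.3 does not say how a count is related to this exposure.

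**The case against.** Much of the case for leaving the text alone is sound.

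- A reader might infer that the plan prescribes a mismatched denominator. It does not. Section 8.6.4 restricts the data to the window, so window person-time is the natural reading. The 36-fold gap measures what is left unstated; it is not an error built into the plan.
- A reader might infer that challenge safety has no usable denominator at all. Section 8.6.1 also gives per-participant measures, and its person-year rate applies only to the primary safety endpoints. General adverse events go through Section 8.6.2 as numbers and percentages of participants. Section 8.6.4.2 uses observed time through Kaplan-Meier and Cox methods, though only up to the first intervention.
- A reader might infer that Section 8.6.4.3 reports undivided totals. It does not say so: Section 8.16 lists mean, median and standard deviation among the summaries. The unit is simply not given.
- A reader might infer that a period with fewer challenges will look safer, or that preschool counts will be 40% lower (3/5) because of the shorter window. The first needs unequal completion, and a challenge rescheduled for an out-of-range starting glucose is not thereby lost. The second needs a constant hourly rate. The documents support neither assumption, and planned exposure is balanced between targets and between bolus types (144 challenges each).
- The contrasts with the run-in might be called harmless because they cannot be computed. Yet a program that divides by all participants in the set would return 0% for the run-in, a zero produced by absent exposure. The sentence still needs correcting.

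What remains is that three repeated steps do not suit window data and that two outputs have no stated exposure unit.

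**Conclusion.** The point holds in limited form. Applied to challenge windows, Section 8.6.4.1 calls for two pairwise contrasts that have no data and a registry comparison over incompatible lengths of time. It also calls for a person-year rate whose time base is unstated. On the natural reading of that base, one event gives an interval from 17 to 3,634 per 100 person-years, which tells the reader little. These figures rest on the planned minimum of 72 completers, all four challenges done and full windows; fewer challenges would shrink the window time further.

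For Section 8.6.4.3, the missing exposure unit is a gap in the specification. Its numerical effect cannot be established from the documents.

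The consequence is bounded: these are secondary, exploratory analyses, and the standard vs lower and late vs normal bolus contrasts remain available. The change is still worth making, because it replaces unworkable steps with better ones at little cost.

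**What to change.** **Section 8.6.4.1**
- Keep the reference to the tabulations of 8.6.2 and to the percent-time definition and paired test of 8.6.3.
- State that the run-in comparison, the registry comparison and the person-year rates are not repeated for challenge-window data.
- Report adverse events arising in the window as number of events, number of participants with an event, and events per 100 challenges started. Counting challenges started keeps in the denominator any challenge cut short by an event.
- Give a 95% confidence interval that allows for up to four correlated challenges per participant.
- Limit contrasts to those between challenges: late bolus feature vs normal bolus, and standard vs lower target. The first needs the two challenges within a period kept separate, whereas the section now averages them.

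**Section 8.6.4.3**
- Report interventions per challenge started, with the number of challenges shown.
- For comparisons, use a count model with offset log(observed challenge hours), clustered by participant.
- When age cohorts are set side by side, also show the first 3 hours for all ages.

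**Cost.** SAP wording and an offset term. Meal times are already logged and CGM data already collected, so no new data or participants are needed. The one downside is that challenge figures no longer share the person-year scale of 8.6.1.
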